**Summary of acceptable pathologic stage for “high risk” Arm D:**

- **Any one of the following features constitutes “high risk” status and will assign the patient to Arm D.**
- **Any T stage with positive margin(s), meaning tumor at the specimen edge that is not superceded by an additional, tumor free margin**
- **“Extensive” ( $> 1$ mm) ECE**
- **$\geq 5$  metastatic lymph nodes) regardless of primary tumor margin status.**
- **Please contact the PI, [name] with any questions or to clarify.**

The adjuvant management plan for high risk HPV-associated oropharyngeal carcinoma patients treated with transoral surgery and neck dissection will be concurrent postoperative CRT to 66 Gy in 33 daily fractions. Concurrent cisplatin will be administered at a dose of 40 mg/m^2 on days 1, 8, 15, 22, 29, 36, 43.

Rev. 6/14, 2/15

5.1.8.3 Definition of Intermediate-Risk Patient Cohort and Management: Arms B-C (5-7 weeks)

Intermediate-risk stratification will be applied when the presence of primary site or neck dissection intermediate-risk pathologic features are identified. **Any one of the pathologic features below will constitute “intermediate risk” and assign the patient to the randomized RT dose arms B or C.**

**Summary of acceptable pathologic stage for “intermediate risk” Arms B or C – randomized RT dose:**

- **Any one of these features constitutes “intermediate risk” status and will assign the patient to Arm B or C.**
- **Any T stage with one or more “close” (<3mm) margin(s)**
- **“Minimal” ( $\leq 1\text{mm}$ ) ECE**
- **1 or more lymph node >3cm in diameter (N2a neck disease).**
- **2-4 lymph nodes positive, any diameter  $\leq 6\text{cm}$  (N2b neck disease), regardless of primary tumor margin status.**
- **perineural invasion**
- **lymphovascular invasion**
- **Please contact the PI, [name] with any questions or to clarify.**

Rev.1/16

The adjuvant management plan for intermediate risk HPV-associated OPSCC patients treated with transoral surgery and neck dissection will be postoperative RT alone. Patients will be randomized to either 60 Gy or 50 Gy fractionated daily over 30 or 25 fractions, respectively. For all patients, bilateral cervical nodal chains and the primary site will be irradiated. For selected patients randomized to 60 Gy, the ipsilateral nodal regions involved with carcinoma and the primary surgical site will receive a 10 Gy boost to a total of 60 Gy

Rev.1/16

Rev. 2/15

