#### 5.1.11.2 Guidelines for Target Volume Delineation

- CTV-P60: CTV-P60 will represent the primary **invasive tumor base**. As the surgery will be transoral, the need to comprehensively treat the surrounding normal tissues that would otherwise be at risk for tumor seeding is not a major consideration. The primary factor influencing the delineation of the CTV-P60 volume should be influenced by the intra-operative assessment of the invasive base of the tumor. These findings should be compared to the preoperative imaging to reconcile any discrepancy. CTV-P60 should **not** include the preoperative intra-luminal extent of the primary tumor that did not invade the oropharyngeal mucosa. This volume shall include a 3-5 mm margin of uncertainty around the estimated extent of the invasive tumor base that is deemed at risk.
- CTV-N60: CTV-N60 will represent the dissected cervical nodal volume found to have nodal metastases. This nodal volume will include the peripheral extent of the sternocleidomastoid muscle laterally and medially, will include a portion of the levator scapulae and the scalene muscles.
- CTV-N50: CTV-N50 will represent the either dissected cervical nodal volumes found not to have nodal

metastases or the undissected contralateral cervical neck when it is treated. This nodal volume will include the peripheral extent of the sternocleidomastoid muscle laterally and medially, will include a portion of the levator scapulae and the scalene muscles. Anteriorly, the posterior aspect of the submandibular gland and the medial pterygoid muscle will be the anterior boundary of level II nodal region.

- a. For the ipsilateral dissected neck, CTV-N50 should be extended to nodal volumes adjacent to pathologically involved nodal volumes. For example, if the neck dissection reveals nodal metastases in level II, the adjacent level I and level V should be included in CTV-N50. This nodal volume will include the peripheral extent of the sternocleidomastoid muscle laterally and medially, will include a portion of the levator scapulae and the scalene muscles.

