- b. Indications for inclusion of the lateral retropharyngeal lymph nodes include the presence of ipsilateral level II nodal metastases or primary tumor extension to involve the posterior pharyngeal mucosa or suspected to be at risk due to involvement of the posterior tonsil pillar mucosa. The ipsilateral lateral retropharyngeal lymph nodes lie medial to the internal carotid artery and are predominantly located at the level of C1 vertebral body and occasionally at the C2 vertebral body level. The medial retropharyngeal lymph nodes are not to be delineated.
- c. The contralateral retropharyngeal lymph nodes will be delineated as part of CTV-N50 when there is clinical/pathologic findings of ipsilateral retropharyngeal lymph node metastases.
- d. For the contralateral undissected neck, CTV-N50, the nodal volume should include the contralateral level II, III and IV nodal regions beginning at the level of the posterior digastric muscle. This nodal volume will include the peripheral extent of the sternocleidomastoid muscle laterally and medially, will include a portion of the levator scapulae and the scalene muscles.
- e. Ipsilateral neck will be permitted, ie. omitting the contralateral CTV-N50 when the mucosal invasive base of the tumor is > 1 cm from the midline mucosa as judged at the time of the surgery. For base of tongue cancers, the primary tumor adverse pathologic features including the positive surgical margins should not be present on the medial tumor

specimen. For base of tongue cancers, the primary tumor should also not demonstrate a deep invading tumor front at the time of the surgery. The distance from the midline mucosa will require documentation including the mucosal surface that is involved when the contralateral CTV-N50 is omitted. Omitting the contralateral neck CTV-N50 is not permitted for N2c tumors and where clinical/pathologic findings of ipsilateral retropharyngeal lymph node metastases.

- CTV-P66: CTV-P66 will represent the region in the primary tumor bed deemed to be at risk due to the presence of a positive involved surgical margin. Typically, this will be at the deep surgical resection margin and thus will not be significantly extending into the pharyngeal lumen.

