#### 5.1.12 IMRT Prescription and Treatment Planning

5.1.12.1 The prescription dose will be administered with a cone-down prescription with daily doses of 2 Gy. No simultaneous in-field boost / dose-painting will be permitted. Treatment will be delivered once daily, 5 fractions per week. Treatment breaks, if necessary, should not exceed 5 treatment days and the reason(s) for the break must be clearly recorded in the treatment record. Any treatment break(s) exceeding two (2) treatment days for reasons other than toxicity/illness will be considered a protocol deviation. The reason for the missed treatment or treatments must be clearly indicated in the copy of the patients treatment record submitted to IROC Rhode Island.

- PTV-N50: will be prescribed 50 Gy in 25 daily fractions
- PTV-P60 or PTV-N60: will be prescribed 60 Gy in 30 daily fractions
- PTV-P66 or PTV-N66: will be prescribed 66 Gy in 33 daily fractions
- PTV-P70 or PTV-N70: will be prescribed 70 Gy in 35 daily fractions

As a cone-down IMRT technique will be used, a dose-summary that represents all the phases of IMRT treatment

planning shall be generated. For example, if the maximum PTV prescription for a patient is to PTV-P66, then the first phase will deliver 50 Gy to both the primary and unilateral (see section 5.1.11.2.e) or bilateral cervical nodal volumes followed by a second phase to the primary surgical bed for an additional 10 Gy and a third phase to the just the boost volume at the site of the positive surgical margin for an additional 6 Gy.

- 5.1.12.2 Tissue Heterogeneity: The dose calculation shall take into account the effect of tissue heterogeneities. The method used for tissue heterogeneity calculations shall be reported. The dose prescription is to be based on a dose distribution corrected for heterogeneities.
- 5.1.12.3 No specific beam arrangements will be specified. Commonly, a co-planar beam arrangement is used.
- 5.1.12.4 Treatment Planning Objectives: The treatment plan(s) used for each patient will be based on an analysis of the volumetric dose, including dose-volume histogram (DVH) analyses of the PTVs and critical normal structures. Inverse optimization algorithms will be used to achieve at least 95% of the volume of the specified PTVs is covered by the prescribed isodose surface while meeting the dose limitations to the delineated OARs.

Priority	Structure Name	Treatment Planning Objective				

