## 9. Statistical Considerations

Rev. 2/15

This is a phase II trial of p16+ (using immunohistochemistry (IHC)) OPSCC patients that will undergo transoral surgery (TOS, Step 1) followed by risk-adjusted radiotherapy (Step 2). Patient risk status is determined after surgical excision and is defined in Section 5.1. Patients with low-risk will be assigned to the observation group (Arm A). Patients with intermediate-risk (the primary study group) will be equally randomized to receive radiotherapy IMRT 50 Gy (Arm B) or 60 Gy (Arm C), stratified by current/former smoking history ( $\leq 10$  vs.  $> 10$  pack-years). Patients with pathological N2C/N3 disease without extensive ECS (and do not meet the high risk feature) will be directly assigned to Arm C receiving IMRT 60 Gy. Patients with high-risk will receive concurrent cisplatin and IMRT 66 Gy (Arm D). Among the first 10 patients enrolled on Arm A, if 2 or more progress or die within 1 year, currently enrolled and subsequently enrolled patients with low risk who have not progressed will be directly assigned to radiotherapy 50 Gy (details are given below).

The study requires 180 evaluable patients with intermediate risk (to be randomized between Arms B/C). Based on results from the interim analysis prepared for the Fall 2015 DSMC meeting, the overall proportion of evaluable patients with intermediate risk is estimated to be 35% (~73% patients are evaluable, among whom ~48% are intermediate risk), which is lower than the originally estimated 48% (80% evaluable, among whom 60% would be intermediate risk). Here, patients who are eligible and started treatment on step 2 are considered as evaluable. As stated in the original design, if the observed proportion of patients with intermediate risk is off over 5% from the anticipated 60%, accrual goal would be adjusted. Therefore, the current section incorporates a sample size increase from the originally proposed 377 to 515 ( $180/0.35=515$ ), to ensure 180 evaluable patients with intermediate risk to be randomized. Based on the observed accrual rate of 18.5 patients per month, this new accrual goal can be achieved in February, 2017.

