#### 9.8 Randomization Scheme

Patients enrolled into this study will be assigned to one of the four treatment arms after transoral surgery based on their histologic risk status. Patients with low-risk will be assigned to the observation group (Arm A). Patients with intermediate-risk will be randomized (with a 1:1 allocation ratio) into either Arm B (IMRT 50 Gy) or Arm C (IMRT 60 Gy). Patients with high-risk will receive post surgery concurrent cisplatin and IMRT 66 Gy (Arm D). The method of permuted blocks will be used for randomization with current/former smoking history ( $\leq 10$  vs.  $> 10$  pack-years) as stratification factor.

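### The radiotherapy text is inconsistent about the randomised doses: the 60 Gy boost is for undefined 'selected' patients, and Arm B's 50 Gy plan is stated nowhere in the planning sections

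*Combined protocol and SAP*

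**What the plan says.** **Assignment.** Section 5.1.8.3 states: "Patients will be randomized to either 60 Gy or 50 Gy fractionated daily over 30 or 25 fractions, respectively". Section 9 says the same, and section 9.8 has intermediate-risk patients "randomized (with a 1:1 allocation ratio) into either Arm B (IMRT 50 Gy) or Arm C (IMRT 60 Gy"). Neither section mentions a subset of Arm C.

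**Boost.** Two sentences after the assignment, section 5.1.8.3 continues: "For selected patients randomized to 60 Gy, the ipsilateral nodal regions involved with carcinoma", together with the primary surgical site, receive a further 10 Gy to reach 60 Gy. No selection rule is given there or elsewhere.

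**Target volumes.** In section 5.1.11.2, "CTV-N60 will represent the dissected cervical nodal volume found to have nodal metastases", and CTV-P60 is the invasive base of the primary. Neither is tied to an arm. The only 50 Gy volume, CTV-N50, covers dissected nodal volumes free of metastases, levels next to involved ones, and the undissected contralateral neck when it is treated.

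**Prescription.** Section 5.1.12.1 lists "PTV-P60 or PTV-N60: will be prescribed 60 Gy in 30 daily fractions" and gives 50 Gy only to PTV-N50. The 66 Gy and 70 Gy volumes are for positive margins, extracapsular extension beyond 1 mm, or gross residual tumour, so they do not concern Arm B.

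**Neck.** Section 5.1.8.3: "For all patients, bilateral cervical nodal chains and the primary site will be irradiated". Section 5.1.11.2(e): "Ipsilateral neck will be permitted, ie. omitting the contralateral CTV-N50", under stated conditions. Section 5.1.12.1 also refers to unilateral or bilateral nodal volumes.

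**Quality assurance.** Section 5.1.17 calls a dose difference of more than 10% from the protocol specification a major deviation.

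**The concern.** Dose is the randomised variable. A site planning an Arm B patient from the volume and prescription sections finds a 60 Gy label for the primary bed and the involved neck, and no 50 Gy label for either. A site planning an Arm C patient from section 5.1.8.3 finds a boost for some patients and no rule for deciding which. If sites resolve these gaps differently, the arms could move closer together in delivered dose, and the per-arm results would describe a mixture.

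Two uses of the results depend on the contrast. Section 9.3 calls the B versus C comparison of 2-year PFS exploratory, but gives it more weight than the other arm comparisons because one randomised arm is likely to go forward. Section 9.5 says that if efficacy is similar, the 50 Gy schedule will be considered for phase III. A smaller dose contrast makes a finding of similarity more likely whatever the true dose effect.

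There is also a reporting problem. Deviations are scored against the protocol specification, and for Arm B the protocol can be read as specifying two different doses.

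**Working it through.** **1. Are the dose figures themselves consistent?** Inputs are from 5.1.8.3 and 5.1.12.1. 60/30 = 2 Gy and 50/25 = 2 Gy per fraction; 50 + 10 = 60 Gy; in the cone-down example, 50 + 10 + 6 = 66 Gy. The arithmetic is sound. The difficulty is which patients and which volumes receive which dose.

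**2. The sections side by side, for intermediate risk.**

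| Item | 5.1.8.3, 9, 9.8 | 5.1.11.2, 5.1.12.1 |
|---|---|---|
| Arm B, primary bed and involved neck | 50 Gy | labelled P60/N60, 60 Gy, no arm condition |
| Arm C, same sites | 60 Gy by assignment; the boost sentence refers to 'selected' patients | P60/N60, 60 Gy |
| Uninvolved or undissected neck | bilateral in everyone (5.1.8.3) | N50, 50 Gy; contralateral side may be omitted |

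No 50 Gy volume for the primary bed or for involved nodes is defined. The nearest text is the cone-down example in 5.1.12.1 (a 66 Gy patient whose first phase gives 50 Gy to the primary and neck) and 5.1.12.5 (a 60 Gy maximum with a 50 Gy first phase). Neither describes a patient whose maximum is 50 Gy.

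**3. How 5.1.17 would score the same plan.**
- 50 Gy delivered in Arm B: 0% from the assignment; against a P60/N60 prescription, 1 − 50/60 = 16.7% low.
- 60 Gy delivered in Arm B: 0% from the P60/N60 prescription; against the assignment, 60/50 − 1 = 20% high.

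Both non-zero differences exceed 10%, so each plan is compliant or a major deviation depending on the section used as the reference.

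**4. What a lost contrast could mean (illustration only).** If a share s of Arm C were not boosted, the mean contrast would be 10 × (1 − s) Gy: 7.5 Gy at s = 25% and 5 Gy at s = 50%. The documents give no s.

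For scale, section 9.3 states power for C versus B of 0.32, 0.62, 0.85 and 0.96 for 85% versus 75%, 70%, 65% and 60% (two-sided Fisher's exact test, 90 per arm, 0.05 level). Exact enumeration gives 0.323, 0.618, 0.848 and 0.959, so the plan's table is reproduced. Now suppose that unboosted Arm C patients have Arm B's rate in the 85% versus 70% case, so that Arm C's rate is 0.85 − 0.15s:

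| s | Arm C rate | Power against 70% |
|---|---|---|
| 0 | 0.850 | 0.618 |
| 10% | 0.835 | 0.510 |
| 25% | 0.8125 | 0.358 |
| 50% | 0.775 | 0.165 |

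**The case against.** The strongest reply is that a radiation oncologist would work out the intent. Sections 9 and 9.8 and the first sentence of the management plan in 5.1.8.3 assign dose without condition. Section 5.1.12.1 requires sequential cone-down delivery, its first phase takes both primary and neck to 50 Gy, and 5.1.12.5 treats the maximum prescription as a property of the patient. Section 5.1.8.3 ties the boost to patients randomised to 60 Gy. Together these suggest that Arm B stops after the first phase. The 66 and 70 Gy prescriptions are also listed without arm names, and nobody would apply them to all patients. On the neck, 5.1.11.2(e) is a conditional exception with a documentation requirement. Section 5.1.16 calls for the prescription sheet for the whole treatment within 3 days of starting radiotherapy, so a misplanned case could be noticed early.

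Much of this stands, and it rules out two stronger readings. A reader might infer that 60 Gy goes only to a selected part of Arm C; the text does not say 'only', and no section describes a 50 Gy subgroup within that arm. A reader might also infer that the protocol directs 60 Gy to Arm B; the cone-down text gives a workable route to 50 Gy. Nor do the documents show that neck volume would differ by arm. The distance from the midline is judged at surgery, before Step 2 randomisation, and differential use of the exception is conjecture.

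What does not fall away is that the randomised treatment of one arm has to be inferred. The 66 and 70 Gy volumes have clinical definitions that exclude ordinary intermediate-risk patients, whereas the P60 and N60 definitions include Arm B's involved sites. 'Selected' has no stated meaning, and the bilateral statement makes no reference to its exception.

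**Conclusion.** The point holds as an internal inconsistency about how the randomised doses are delivered. Arm B's plan is not stated in the planning sections, 'selected' is undefined, and the neck statements disagree. The demonstrable consequence is that dose scoring under 5.1.17 is ambiguous: 16.7% or 20% against a 10% limit, depending on the reference.

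Any loss of dose contrast is of unknown size. The 7.5 and 5 Gy figures and the reduced power rest on an assumed share s, and the power figures also assume that unboosted patients have Arm B's PFS rate. The documents do not show that any patient was misplanned. The primary rule in 9.3 judges each arm separately by whether the upper limit of its 90% confidence interval exceeds 85%, so the dilution arithmetic does not apply directly to it. It bears mainly on the exploratory B versus C comparison and the choice of arm for phase III. The sample size and power table are correct as computed. The change should be made because it is cheap and concerns the randomised variable.

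**What to change.** Reconcile 5.1.8.3, 5.1.11.2 and 5.1.12.1 so that, for each arm, the named volumes and their prescriptions match the randomised assignment. Define 'selected' or remove it. In 5.1.8.3, cross-reference the contralateral-neck exception in 5.1.11.2(e). State in 5.1.17 that dose deviations are scored against the assigned arm. Which volumes and doses are right is for the clinical team; the request is only that the sections agree.

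The cost is a protocol clarification and an update of the radiotherapy quality-assurance checklist. If accrual is already complete (section 9.2 projected February 2017), the same reconciliation is still needed so that delivered dose can be scored and reported by arm on a single definition.

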#### 5.1.8.4 Definition of Unknown-Risk Patient Cohort and Management: Arm C (5-7 weeks)

Patients found to have N2C or N3 disease on final pathologic analysis are at unknown risk for recurrence, but are not candidates for deintensified adjuvant therapy in this trial. These patients will be treated on Arm C.

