3.2 Registration/Randomization to Step 2 - Arms A, B, C, and D

Rev. 6/14

- \_\_\_\_\_ 3.2.1 Histopathologic assessment of surgical pathology must include examination for perineural invasion (PNI) and lymphovascular invasion (LVI) and reported as absent or present. The absence or presence of extracapsular extension (ECE) requires gross and microscopic assessment and is defined to be:
- absent (negative or nodal metastasis with smooth/rounded leading edge confined to thickened capsule/pseudocapsule),
  - present - minimal (tumor extends  $\leq$  1 mm beyond the lymph node capsule), or
  - present - extensive (Gross, tumor extends  $>$ 1 mm beyond the lymph node capsule (includes soft tissue metastasis)

Rev. 2/15  
Rev. 1/16

- \_\_\_\_\_ 3.2.2 Patient must be stratified/classified into one of the following risk categories:
- The highest risk feature assessed pathologically will determine the patient's category/treatment arm assignment.
- Low Risk: T1-T2, N0-N1 AND clear ( $\geq$  3mm) margins, AND no ECE or PNI/LVI.
  - High Risk: Any of the following features: one or more positive margin(s) with any T stage, OR "Extensive" ( $>$  1mm) ECE, OR  $\geq$  5 metastatic lymph nodes (regardless of primary tumor margin status).
  - Intermediate Risk: Any of the following features: one or more "close" ( $<$  3mm) margin(s), OR "Minimal" ( $\leq$  1mm) ECE, OR N2a (1 or more lymph node  $>$  3cm in diameter), OR N2b (2-4 lymph nodes positive, any diameter  $\leq$  6cm), OR with perineural invasion or lymphovascular invasion.
  - Unknown Risk: Patients found to have N2C or N3 disease on final pathologic analysis are at unknown risk for recurrence, but are not candidates for deintensified adjuvant therapy in this trial. These patients will be treated on Arm C.
  - **Patients not categorized into the appropriate risk category will be considered ineligible for the study.**

Rev. 1/16

Rev. 2/15  
Rev. 9/16

- \_\_\_\_\_ 3.2.3 Patient must be registered/randomized to Step 2 within a maximum of 7 weeks following surgery.
- \_\_\_\_\_ 3.2.4 Women of childbearing potential and sexually active males are strongly advised to use an accepted and effective method of contraception

\_\_\_\_\_  
Physician Signature

\_\_\_\_\_  
Date

**OPTIONAL:** This signature line is provided for use by institutions wishing to use the eligibility checklist as source documentation.

Rev. Add8

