4.2.4 Stratification and Classification Factors

4.2.4.1 Classification Factors

- The highest risk feature assessed pathologically will determine the patient's category/treatment arm assignment.
  - Low Risk: T1-T2, N0-N1, with clear ( $\geq 3$ mm) margins, and without any ECE or PNI/LVI.
  - High Risk: Any T stage with positive margin(s), meaning tumor at the specimen edge, not superceded by an additional, tumor free margin, OR "Extensive" ( $> 1$ mm) ECE, OR  $\geq 5$  metastatic

Rev. 7/13

Rev. 2/15

Rev. 6/14

Rev. 1/16

lymph nodes, regardless of primary tumor margin status.

- Intermediate Risk: Any T stage with one or more “close” (<3mm) margin(s) OR “Minimal” (≤ 1mm) ECE, OR 1 or more lymph node >3cm in diameter (N2a neck disease), OR 2-4 lymph nodes positive, any diameter ≤ 6cm (N2b neck disease (regardless of primary tumor margin status)], OR with perineural invasion or lymphovascular invasion.
- Unknown Risk: Pathologic N2c (bilateral nodes), OR Pathologic N3 (> 6cm node)

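### The protocol gives pN2c/N3 patients conflicting arm assignments, never ranks the unknown-risk category, and defines their first-ten safety cohort in two ways

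*Combined protocol and SAP*

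**What the plan says.** **Unknown risk.** Section 5.1.8.4 states: "Patients found to have N2C or N3 disease on final pathologic analysis are at unknown risk for recurrence". It then gives the arm: "These patients will be treated on Arm C". The Step 2 checklist in Section 3.2.2 says the same, that they "are not candidates for deintensified adjuvant therapy in this trial. These patients will be treated on Arm C". Neither place makes an exception. Section 4.2.4.1 lists the category but names no arm.

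**Section 9, opening text.** Here the assignment is conditional: "Patients with pathological N2C/N3 disease without extensive ECS (and do not meet the high risk feature) will be directly assigned to Arm C".

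**High risk (5.1.8.2).** Any one of a positive margin, ECE beyond 1 mm, or five or more positive nodes confers high-risk "status and will assign the patient to Arm D".

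**Intermediate risk (5.1.8.3).** Any one listed feature leads to randomisation between B and C. The list includes close margins, minimal ECE, PNI, LVI, two to four positive nodes (labelled N2b) and "1 or more lymph node >3cm in diameter (N2a neck disease").

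**Precedence.** Sections 3.2.2, 4.2.4.1 and 5.1.8 share one rule: "The highest risk feature assessed pathologically will determine the patient's category/treatment arm assignment".

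**Randomisation (9.8).** It covers low, intermediate and high risk, and has no pN2c/N3 rule.

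**Safety rule.** If two or more of ten patients progress or die within a year, pN2c/N3 patients move to the Arm D treatment. The table in Section 9.1 applies this to the first ten with pN2c/N3 disease. Section 9.3 applies it to those directly assigned to Arm C, expected to be 5% of the total population.

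**The concern.** The sections that sites use to choose an arm do not carry the condition in Section 9, and the precedence rule works only between categories that have an order. Unknown risk has none.

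Three things depend on how a site resolves this:

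- **Treatment received.** The competing instructions differ in radiation dose and in the use of cisplatin.
- **Who is randomised.** Section 9 counts randomised intermediate-risk patients toward the 180. A pN2c/N3 patient with a close margin is inside or outside that count depending on the section followed. Section 3.2.2 also makes a patient who is not placed in the appropriate category ineligible, and Section 9.3 analyses only eligible patients.
- **The safety rule.** Its population depends on whether pN2c/N3 patients with high-risk features are among the ten.

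**Working it through.** **1. The instructions side by side**

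| pN2c/N3 patient with | One instruction | Competing instruction |
|---|---|---|
| a high-risk feature | Arm C (3.2.2, 5.1.8.4) | Arm D (5.1.8.2; consistent with the condition in Section 9) |
| intermediate features only | Arm C directly (3.2.2, 5.1.8.4, Section 9) | randomised B/C (5.1.8.3) |
| neither | Arm C | none |

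High outranks Intermediate under the precedence rule, so no patient has more than two live instructions.

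**2. How far the categories overlap**

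The written rules were applied to every combination of nodal pattern with margin (3 levels), ECE (3) and PNI/LVI (2), that is 18 combinations per nodal pattern.

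- Bilateral N2c: 2 node counts × 2 sizes × 18 = 72
- Single contralateral N2c: 1 × 2 × 18 = 36
- N3: 3 node counts × 1 size × 18 = 54
- Total: 162

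| Reading of the nodal criteria | High feature present | Intermediate only | Neither |
|---|---|---|---|
| Size and count taken literally | 107 + 7 = 114 | 47 | 1 |
| N2a/N2b labels limit the criteria | 84 + 30 = 114 | 42 | 6 |

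On nodal findings alone (clear margins, no ECE, no PNI/LVI) there are nine patterns. Read literally, eight of the nine meet a high or intermediate rule. With the labels applied, only the three with five or more nodes do. These are unweighted pattern counts, not patient proportions.

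**3. Size of the group**

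Inputs are 5% (Section 9.3), 515 registered and about 376 evaluable (Section 9.2).

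- 0.05 × 515 = 25.75, about 26
- 0.05 × 376 = 18.8, about 19

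This is the group directly assigned to Arm C.

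**4. The safety rule**

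The plan's table is P(X ≥ 2), X ~ Bin(10, p) = 1 − (1 − p)^10 − 10p(1 − p)^9.

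| p | 0.10 | 0.15 | 0.20 | 0.25 | 0.30 |
|---|---|---|---|---|---|
| Plan | 0.26 | 0.46 | 0.62 | 0.76 | 0.85 |
| Recomputed | 0.264 | 0.456 | 0.624 | 0.756 | 0.851 |

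The table reproduces with p as the one-year event rate, although its row is labelled as a PFS rate.

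Illustration, assuming 25% one-year failure for high-risk members of the ten and 10% for the rest:

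- Three high-risk: P(0) = 0.9^7 × 0.75^3 = 0.2018; P(1) = 0.2018 × (7/9 + 3/3) = 0.3587; P(≥2) = 0.44
- Five high-risk: P(0) = 0.9^5 × 0.75^5 = 0.1401; P(1) = 0.1401 × (5/9 + 5/3) = 0.3114; P(≥2) = 0.55

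**The case against.** The strongest defence is that the texts can be read together. No category is named above High, 5.1.8.2 sends any high-risk feature to Arm D, and the precedence rule appears three times. A site reading all of this would probably reach the Section 9 result for High against Unknown. For Intermediate against Unknown, the statement that these patients are not candidates for de-intensified therapy argues strongly against randomisation that could give 50 Gy. Sections 5.1.8.2 and 5.1.8.3 also refer questions to the study PI.

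This weakens several readings that a reader might infer:

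- **Site-facing text sends every pN2c/N3 patient to 60 Gy alone.** It does not, because the precedence and Arm D rules are site-facing too.
- **One patient can fall under three dose assignments.** This needs the precedence rule to be ignored.
- **Nearly all such patients meet another rule on nodal findings.** This fails if the N2a/N2b labels govern. Section 3.2.2 leads with those labels, and Appendix III defines N2a and N2b as ipsilateral and at most 6 cm. Overlap then depends on margins, ECE, PNI/LVI or five or more nodes, and no frequencies are given for these among pN2c/N3 patients.
- **The 13 of 104 potentially misclassified patients in Section 9.3 are evidence.** No cause is stated for them.
- **Applying the trial-wide 32% high-risk share to the 5% gives the number affected.** Section 9.3 describes the 5% as directly assigned to Arm C, a group that under Section 9 has no high-risk features.

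The illustrated mixtures also average only 14.5% and 17.5% failure, inside the range the plan already tabulates.

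What the defence does not remove is the unconditional wording in 3.2.2 and 5.1.8.4, the lack of a pN2c/N3 exclusion in 5.1.8.3, and the two definitions of the interim cohort. A consistent reading is possible, but it is not stated, and a site could equally treat 5.1.8.4 as the specific rule for these patients.

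**Conclusion.** The concern holds as a conflict in an operative assignment rule. Each pN2c/N3 patient with a high-risk or intermediate feature has two competing instructions, and the protocol does not say which governs. The first-ten cohort differs between Sections 9.1 and 9.3 whenever a pN2c/N3 patient is sent to Arm D.

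The directly assigned group is about 19 to 26 patients, depending on whether the 5% refers to evaluable or registered patients. The documents do not allow the number with high-risk features to be calculated. The rise in trigger probability from 0.26 to 0.44 or 0.55 is illustrative only, since both the mix and the 25% failure rate are assumed. No sample size, alpha or power figure is affected, and no view is taken on which treatment rule is right.

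**What to change.** - Reconcile Sections 3.2.2, 4.2.4.1, 5.1.8.2, 5.1.8.3, 5.1.8.4, the opening of Section 9, and 9.8 so that all state one order of precedence among High, Unknown and Intermediate. The study chairs decide the order.
- State whether the N2a and N2b labels limit the nodal criteria in the intermediate list.
- Define the first-ten pN2c/N3 cohort in identical terms in Sections 9.1 and 9.3, on the population that the chosen order produces.
- For patients already enrolled, report which rule was applied: pN2c/N3 patients by presence of high-risk or intermediate features, arm assigned, and whether counted in the first ten.

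The cost is a wording amendment, an updated Step 2 checklist and one tabulation of surgical pathology against arm. No patients are added, and no dose or clinical criterion is proposed here.
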